#### **2.2.6.1. Phase 1/2 Study in Participants with Amyotrophic Lateral Sclerosis**

A Phase 1/2, open label, single center study in 18 Participants diagnosed with clinically definite, clinically probable, or clinically probable-laboratory supported ALS (VMALS-001; NCT02039401) lasting 9 months was completed. Prior to injections on Day 0, Participants were assessed using the Revised Amyotrophic Lateral Sclerosis Functional Rating Scale (ALSFRS-R), the Medical Research Council (MRC) scale for muscle strength testing, dynamometry, forced vital capacity (FVC), and muscle circumference.

All Participants (18 Participants) received a total of 64 mg of VM202 IM in the upper limbs (abductor pollicis brevis, first dorsal interosseous, biceps, deltoid, extensor carpi radialis, flexor carpi ulnaris, and flexor carpi radialis) and lower limbs (quadriceps, gastrocnemius, and tibialis anterior).

Engensis was administered over the course of four visits: Days 0, 7, 14, and 30. As in previous Engensis studies, the final dose of VM202 for each target muscle group was divided and administered 2 weeks apart with injection of the upper limbs at separate visits from injection of the lower limbs.

Post-injection, ALSFRS-R, FVC, and muscle strength (as determined by the MRC scale) were assessed at Days 30, 60, and 90, and at 6 and 9 months. Muscle circumference and dynamometry were conducted on Days 60 and 90, and at 6 and 9 months. Participants were contacted through 36 months by phone to assess survival.

[figure not shown]
After Engensis or Placebo injections through Day 30, seventeen (17) Participants completed the 9-month follow-up; one Participant died prior to the 9-month visit. Three (3) Participants completed the study (36-month follow-up), while 14 Participants died following the 9-month visit; all deceased Participants died due to respiratory failure associated with ALS. Four additional serious adverse events (SAEs) that required hospitalization were reported. All deaths and SAEs were classified as unrelated to the study drug. Injection site reactions were limited to pain and/or bruising.

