## **8.5. Adverse Events and Serious Adverse Events**

The definitions of AEs, TEAEs, SAEs and TESAEs can be found in Section [10.2](#), Appendix 2.

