### **8.5.3. SAE Reporting to the Sponsor or Designee**

All SAEs should be reported to the Sponsor or designee within 24 hours of knowledge of the SAE occurring.

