#### **8.5.4.2. Other Medical Problems in ALS Patients**

Several medical problems are frequently observed in patients with ALS that should be considered AESIs. These medical problems are listed below.

- Pulmonary Medical Problems: Because patients with ALS are at an increased risk to develop pulmonary medial problems such as aspiration of food or liquids, pneumonia,

---

and respiratory arrest, all events of this type that occur after randomization will be considered AESIs.

- **Progressive Muscle Weakness:** Because some patients with ALS may develop rapidly progressive muscle weakness that results in loss of ability to care for self, decubitus ulcers, or weight loss due to impaired deglutition, all events of this type that occur after randomization will be considered AESIs.
- **Bulbar Disease:** Participants may develop bulbar disease or worsening on bulbar disease following randomization manifested as challenges with dysarthria, facial weakness, impaired tongue pulsion or palate elevation, and impaired mastication and swallowing; all of these types of events that occur after randomization will be considered AESIs.

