#### **8.5.9. Disease-Related Events and/or Disease-Related Outcomes Not Qualifying as AEs or SAEs**

Except for signs and symptoms of ALS (i.e., numbness, pain, tingling or burning sensation, cramps, and increased sensitivity to touch), all disease-related events or disease-related outcomes qualify as AEs or SAEs.

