#### 9.3.1. Primary Endpoints

Safety analyses in this study will evaluate the safety profile of Engensis as compared with Placebo. The primary endpoints for safety are as follows:

- Incidence of TEAEs and TESAEs for Engensis compared to Placebo
- Incidence of injection site reactions for Engensis compared to Placebo
- Incidence of clinically significant laboratory values for Engensis compared to Placebo

No formal statistical testing will be conducted for the safety analyses. All Participants in the safety subset will be included in these analyses. Participants will be grouped by treatment received. All summaries will be derived based on available data. No imputation will be performed for missing values. All safety analyses will be made on the Safety Population.

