**Events NOT Meeting the AE Definition**

- Any clinically significant abnormal laboratory findings or other abnormal safety assessments that are associated with the underlying disease, unless judged by the Investigator to be more severe than expected for the Participant's condition.
- The disease/disorder being studied or expected progression, signs, or symptoms of the disease/disorder being studied, unless more severe than expected for the Participant's condition.
- Medical or surgical procedure (e.g., endoscopy, appendectomy): the condition that leads to the procedure is the AE.
- Situations in which an untoward medical occurrence did not occur (social and/or convenience admission to a hospital).

- Anticipated day-to-day fluctuations of pre-existing disease(s) or condition(s) present or detected at the start of the study that do not worsen.

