#### 10.2.3. Definition of SAE

If an event is not an AE per the definition above, then it cannot be an SAE even if serious conditions are met (e.g., hospitalization for signs/symptoms of the disease under study, death due to progression of disease).

An SAE is defined as any untoward medical occurrence that, at any dose:

a. Results in death

b. Is life-threatening

The term “life-threatening” in the definition of “serious” refers to an event in which the Participant was at risk of death at the time of the event. It does not refer to an event, which hypothetically might have caused death, if it were more severe.

c. Requires inpatient hospitalization or prolongation of existing hospitalization

- In general, hospitalization signifies that the Participant has been detained (usually involving at least an overnight stay) at the hospital or emergency ward for observation and/or treatment that would not have been appropriate in the physician’s office or outpatient setting. Complications that occur during hospitalization are AEs. If a complication prolongs hospitalization or fulfills any other serious criteria, the event is serious. When in doubt as to whether “hospitalization” occurred or was necessary, the AE should be considered serious.
- Hospitalization for elective treatment of a pre-existing condition that did not worsen from Baseline is not considered an SAE.

d. Results in persistent disability/incapacity 

• The term “disability” means a substantial disruption of a person’s ability to conduct normal life functions.

• This definition is not intended to include experiences of relatively minor medical significance such as uncomplicated headache, nausea, vomiting, diarrhea, influenza, and accidental trauma (e.g., sprained ankle), which may interfere with or prevent everyday life functions but do not constitute a substantial disruption.

e. Is a congenital anomaly/birth defect

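### Protocol 8.5.9 counts expected ALS progression as an AE or SAE and Appendix 2 does not, so TESAE incidence, a primary endpoint, depends on which section a site follows

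*Protocol*

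**What the plan says.** Protocol 8.5.9 sets aside a list introduced by i.e. (numbness, pain, tingling or burning, cramps, heightened sensitivity to touch) and then says that "all disease-related events or disease-related outcomes qualify as AEs or SAEs".

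Appendix 2 takes another line. Among the events that do not meet the AE definition, Section 10.2.1 lists the disease under study or its "expected progression, signs, or symptoms of the disease/disorder being studied, unless more severe than expected" for that participant. Section 10.2.3 opens by saying that if an event is not an AE, "it cannot be an SAE even if serious conditions are met (e.g., hospitalization for signs/symptoms of the disease under study, death due to progression".

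Three places point to Appendix 2. Section 8.5 says "The definitions of AEs, TEAEs, SAEs and TESAEs can be found in Section" 10.2, Section 8.5.1 refers there for the TEAE definition, and Section 8.5.2 refers there for recording and causality assessment. None says that Appendix 2 overrides 8.5.9.

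Section 8.5.4.2 adds a further rule. For pulmonary problems, progressive weakness and bulbar disease it provides that such events after randomization are AESIs; for the pulmonary group the words are "all events of this type that occur after randomization will be considered AESIs". It makes no exemption for expected progression.

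SAP 6.14.1 restates the AE and SAE definitions without the progression exclusion and without the opening sentence of Section 10.2.3.

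The first primary endpoint in Protocol 9.3.1, repeated in SAP 3.1, is "Incidence of TEAEs and TESAEs for Engensis compared to Placebo".

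**The concern.** ALS progresses during follow-up, so hospitalization or death from the disease is a foreseeable event in both arms. Two sites could see the same hospitalization, both judge it expected progression, and classify it differently while each follows the protocol. One would record a TESAE and the other would record no adverse event.

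Three things are at stake:

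- **The primary count.** TESAE incidence would mix two definitions across sites.
- **Expedited reporting.** Section 8.5.3 requires that "All SAEs should be reported to the Sponsor or designee within 24 hours of knowledge of the SAE occurring". Whether the clock starts depends on the classification.
- **Oversight and listings.** The SAE and TESAE material reviewed by the DSMB (Protocol 10.1.5.1), the TESAE tables and Listing 16.2.7.7 all inherit the same ambiguity.

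**Working it through.** The plan gives no event rate, power or test for safety, so there is no stated figure to reproduce. The check is a comparison of the texts, followed by the weight of one participant.

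**Step 1. Apply each rule to the same event.**

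| Event after first injection | Protocol 8.5.9 | Appendix 2 (10.2.1, 10.2.3) | Agree? |
|---|---|---|---|
| Hospitalization for progression, worse than expected | SAE | SAE | Yes |
| Hospitalization for progression, judged expected | SAE | Not an AE, so not an SAE | No |
| Death from progression, judged expected | SAE | Not an AE, so not an SAE | No |
| Non-serious weakness or bulbar worsening, judged expected | AE | Not an AE | No |

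Reading the 8.5.9 exception more widely does not remove the conflict. Even if its list were only illustrative, it concerns signs and symptoms. Death is an outcome, and 8.5.9 expressly includes disease-related outcomes.

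**Step 2. Look for a tie-breaker.**

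- The pointers in 8.5, 8.5.1 and 8.5.2 say where definitions and methods are found. They state no precedence, and 8.5.9 sets its own rule in the same chapter.
- Section 8.5.4.2 fits 8.5.9 better than 10.2.1. If it governs, the event is an adverse event and the bar in 10.2.3 does not apply. If 10.2.1 governs, the event is not an adverse event and so cannot be an AESI. AE, AESI and SAE status are therefore all open together.
- SAP 6.14.1 defines an SAE as an AE meeting a seriousness criterion. It does not say whether expected progression is an AE.

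**Step 3. Weight of one participant.** Inputs: 12 Engensis and 6 Placebo (Protocol 5.3), assuming all are dosed as randomized. Let k be the number of participants in an arm of size n whose only serious event is expected progression.

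- Shift in TESAE incidence = k/n under 8.5.9, and 0 under Appendix 2.
- Engensis, k = 1: 1/12 = 8.3 points.
- Placebo, k = 1: 1/6 = 16.7 points.
- A participant with any other TESAE already counts, so the shift is 0.

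**Step 4. Illustration with assumed counts and no other TESAEs.**

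- One such participant per arm: 8.3% against 16.7% under 8.5.9 (difference -8.3 points), and 0% against 0% under Appendix 2.
- Three Engensis and one Placebo: 3/12 = 25.0% against 16.7% (difference +8.3 points), and again 0% against 0%.

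The same steps apply to any-TEAE incidence, but only for a participant with no other TEAE.

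**The case against.** The best defence is that Appendix 2 is the default. Three sections refer to it, and a site looking for a definition would go there. That makes it a plausible working rule. It does not cancel 8.5.9, a specific instruction on exactly this class of event.

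A second defence is that the consequence is limited. This stands in part. Protocol 9.3.1 plans no formal safety testing, so there is no type I error or power question. Deaths would not disappear: they appear in the all-cause mortality outputs (SAP 6.15.8, Table 14.6.9 and Listing 16.2.9.8), under the death-narratives heading 14.3.3 in SAP 11, and in the pooled mortality data the DSMB reviews. Hospitalizations for expected progression have no equivalent route.

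A third defence is that AESI capture leaves only the seriousness label open. It fails for the reason in Step 2: under 10.2.1 the event is not an adverse event at all.

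Two stronger readings are tempting, and the documents do not support them.

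- A reader might infer that the earlier ALS study counted a progression death as an SAE, so that the two studies are not comparable. Protocol 2.2.6.1 says "all deceased Participants died due to respiratory failure associated with ALS", and one death before nine months plus four additional SAEs equals the five in the Synopsis. But the four are described after all the deaths, including 14 later ones, and deaths and SAEs are then named separately. That study's SAE rules are not given.
- A reader might scale its one early death in 18 to a chance that this endpoint changes. That would give the chance of any death, not of one judged expected in a participant with no other TESAE, and it would rest on a single event.

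**Conclusion.** The contradiction holds and is in current protocol text. For events judged to be expected ALS progression, 8.5.9 and Appendix 2 give opposite answers, and neither the protocol nor the SAP says which governs.

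The size is 8.3 points of TESAE incidence per affected Engensis participant and 16.7 points per affected Placebo participant. This assumes 12 and 6 dosed as randomized and that the affected participant has no other TESAE. How many participants would be affected cannot be derived from the documents. No direction of bias is claimed, because events in either arm could be classified either way.

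This should be fixed. It changes what a primary endpoint counts and when expedited reporting applies, but it does not invalidate the design. Which rule is right is for the sponsor to decide.

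**What to change.** Reconcile Protocol 8.5.4.2, 8.5.9, 10.2.1 and 10.2.3 with SAP 6.14.1 into one recording rule for events consistent with ALS progression, applied at every site. The sponsor should choose the rule before unblinding and apply it to events already recorded as well.

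Cross-check every death in Listing 16.2.9.8 against Listing 16.2.7.7 and explain any difference. The first uses the ITT Population and the second the Safety Analysis Population, so a mismatch is not automatically an error.

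Optionally, add a yes/no progression flag and show TESAE incidence with and without flagged events.

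The cost is wording in four protocol places and one SAP section, plus the listing check. The optional flag adds one eCRF field and extra table rows. If the inclusive rule is chosen, more events will be recorded in both arms.

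One separate item should not be folded into this one: Schedule of Activities footnote 5 sends examination abnormalities to AE recording whether or not they are clinically significant, while Section 10.2.1 requires clinical significance.

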### **8.6. Study Completion**

#### **8.6.1. End of Study Definition**

The end of the study is defined as the date on which the last Participant in the study completes the Day 180 Visit or is discontinued.

#### **8.6.2. Completed Participants**

A Participant is considered to have completed the study if the Participant completes all phases of the study including the last Visit on Day 180 or the last scheduled procedure shown in the SoA.

---

## 9. STATISTICAL CONSIDERATIONS

Detailed statistical methods are described in the Statistical Analysis Plan (SAP).

### 9.1. Sample Size Determination

A sample size of 18 Participants was chosen for safety assessments and preliminary evaluation of exploratory endpoints.

### 9.2. Population for Analysis: Safety Population

The safety analysis population will contain all Participants who are randomized and receive at least one Study Injection. Participants will be grouped according to their actual treatment received, not according to their randomization assignment (as randomized). Participants treated with any Engensis dose will be grouped in the Engensis group; Participants treated without any Engensis will be grouped in the Placebo group.

### 9.3. Statistical Analyses

The SAP will be finalized prior to database lock and will include a more technical and detailed description of the statistical analyses described in this section. This section is a summary of the planned endpoints.

#### 9.3.1. Primary Endpoints

Safety analyses in this study will evaluate the safety profile of Engensis as compared with Placebo. The primary endpoints for safety are as follows:

- Incidence of TEAEs and TESAEs for Engensis compared to Placebo
- Incidence of injection site reactions for Engensis compared to Placebo
- Incidence of clinically significant laboratory values for Engensis compared to Placebo

No formal statistical testing will be conducted for the safety analyses. All Participants in the safety subset will be included in these analyses. Participants will be grouped by treatment received. All summaries will be derived based on available data. No imputation will be performed for missing values. All safety analyses will be made on the Safety Population.

#### 9.3.2. Exploratory Endpoints

The exploratory endpoints include:

- Change from Baseline (Day 0) in total mean ALSFRS-R scores at Day 180 for Engensis compared to Placebo

---

- Change from Baseline (Day 0) in ALSFRS-R subscores for Fine and Gross Motor Functions (sum of scores for items 4 to 9) and for Bulbar Function (sum of scores for items 1 to 3) on Days 30, 60, 84, 120, 144, and 180 for Engensis compared to Placebo
- Changes in the slope of the total ALSFRS-R score over time for Engensis compared to Placebo
- Change from Baseline (Day 0) in muscle strength assessed bilaterally by HHD in muscles in the upper and lower extremities on Days 30, 60, 84, 120, 144, and 180 for Engensis compared to Placebo
- Change from Baseline (Day 0) in the ATLIS tests, where available, at Days 30, 60, 84, 120, 144, and 180 for Engensis compared to Placebo
- Change from Baseline (Day 0) in QoL using the ALSAQ-40 on Days 84 and 180 for Engensis injections compared to Placebo
- PGIC and CGIC at Days 84 and 180 for Engensis compared to Placebo
- Change from Baseline (Day 0) in SVC on Days 30, 60, 84, 120, 144, and 180 for Engensis compared to Placebo
- Time to tracheostomy for Engensis compared to Placebo
- Time to all-cause mortality by Day 180 for Engensis compared to Placebo
- Change from Baseline (Day 0) in biomarkers for muscle atrophy in biopsies collected before and after injections for Engensis compared to Placebo

#### **9.4. Data Safety Monitoring Board**

An independent Data Safety Monitoring Board (DSMB) will periodically review blinded (noncomparative) data as a limited set of unblinded tables and/or listings, including all reported AEs and SAEs. The objectives of the DSMB meetings are to review the safety outcomes of the study and provide guidance to study sponsor regarding the safety of Engensis. The data analyses for the DSMB meetings will be directly provided to the DSMB members, and no data will be released to the study sponsor or blinded designees. No adjustment will be made for multiple testing due to the DSMB data review. Further details of DSMB responsibilities are included in the DSMB Charter.

---

**10. SUPPORTING DOCUMENTATION AND OPERATIONAL CONSIDERATIONS****10.1. Appendix 1. Regulatory, Ethical, and Study Oversight Considerations****10.1.1. Regulatory and Ethical Considerations****10.1.1.1. Institutional Review Board**

Prior to the initiation of the study, the protocol, the informed consent form, and Investigator's Brochure will be submitted to the IRB for approval. By signing the "Statement of Investigator" form (Form FDA 1572), the Investigator is ensuring that an IRB compliant with the requirements set forth in 21 CFR 56 will be responsible for the initial and continuing review of the proposed clinical study. A copy of the IRB approval letter for the protocol, the informed consent, and the protocol signature page must be submitted to the Sponsor prior to release of investigational supplies to the Study Site. The approval letter must refer to the specific protocol and the informed consent form. The Study Site must maintain an accurate and complete record of all reports, documents, and other submissions made to the IRB concerning this protocol. A list of the IRB members, their titles or occupations, and their institutional affiliation, or an IRB assurance number must be provided to the Sponsor prior to release of study supplies.

Health authority regulations require that all advertisements for Participant recruitment be approved by an IRB prior to implementation. The complete text and format must be submitted to the Sponsor for approval prior to IRB submission.

The Investigator is responsible for notifying the IRB of any SAEs as required by the IRB. A copy of the notification must be forwarded to the Sponsor or its designee.

Status reports must be submitted to the IRB at least once a year (or more frequently as required by the IRB), and the IRB must be notified of completion or termination of the study.

**10.1.1.2. Informed Consent Process**

The Investigator has the responsibility to inform each Participant, prior to the Screening evaluation, of the purpose of this clinical study, including possible risks and benefits, and document the informed consent process in the Participant's chart. An informed consent form containing the required elements of informed consent must be generated by the Investigator. After approval by the Sponsor, the informed consent form (ICF) must be submitted to and approved by an IRB. Prior to entry into the study or initiation of any study-related procedures, the Participant must read, sign, and date the ICF. The person executing the consent must also sign and date the IRB-approved ICF. One original ICF is to be retained by the Study Site, and a copy is to be given to the Participant. The informed consent process must be documented in the Participant's source/medical record.

The ICF must be written in a language in which the Participant is fluent. If a foreign language translation is required, a statement of certification of the translation must be issued. Regulations require that foreign language ICFs be submitted to the IRB for approval. The Investigator must

---

forward a copy of the ICF, the certified foreign language translation, and an IRB approval letter to the Sponsor.

The Investigator will explain the study purpose, procedures, and Participant's responsibilities to the Participant. The Participant's willingness and ability to meet the follow-up requirements will be determined and written informed consent will be obtained. The Participant will sign and date the ICF. The Investigator or a qualified designee will also sign and date the ICF. The original ICF will be retained with the Participant's records; a copy will be provided to the Participant.

If the ICF is amended during the study, the Investigator or a qualified designee must follow all applicable regulatory requirements pertaining to approval of the amended ICF by the IRB. For each new version of the ICF, the IRB will be consulted to determine if Participants who have not completed the study must be re-consented to the new ICF.

